## **I. Introduction**

This document describes the statistical analysis plan for mainline analyses for the REGAIN Randomized Trial (Regional vs General Anesthesia for Promoting Independence after Hip Fracture, NCT02507505) related to the primary study outcome and secondary/exploratory outcomes related to medical complications, functional recovery, and health care utilization up to approximately 60 days after randomization. Analyses related to other secondary and exploratory outcomes are described in separate documents. For information on the background, design, and methods of the REGAIN study, please refer to the full study protocol.

## **II. Quality Control Prior to Unblinding**

Prior to unblinding, we will review the distributions of each variable to be included in the analysis, aggregated across treatment arms, to identify any outlying values that may be inaccurate and should be checked. To the extent possible, inaccuracies will be resolved and the database updated with the correct values. Data that are clearly incorrect but cannot be corrected will be excluded from the analyses. Data that are unusual but not impossible, and cannot either be verified or corrected, will remain in the analysis.

## **III. Baseline and Intraoperative Data**

Baseline demographic and clinical variables will be examined to evaluate general trends and determine whether there are any notable imbalances that may lead to secondary adjustments. Continuous variables will be summarized through standard measures of central tendency and spread including means, medians, standard deviations and interquartile ranges (IQRs). Frequency distributions will be calculated for categorical variables.

Intraoperative data, including surgery and anesthesia characteristics, will be summarized similarly.

## **IV. General Principles**

All analyses (primary, secondary, exploratory) will adjust for the 2 binary stratification factors, namely sex, fracture type (intracapsular, extracapsular), and country (U.S., Canada sites). Sex, fracture type, and site were the original stratification factors for randomization assignment, but with 46 participating sites, some with very few enrolled subjects, it will not be possible to include site in the stratified analysis. Because there might be systematic differences in health care and insurance use between Canada and U.S. sites, we will add country as an additional stratification factor. We will perform descriptive analyses of results by site to see whether there appear to be any major site-specific effects. Analyses will follow a modified intention-to-treat principle, with sensitivity analyses performed to assess the potential impact of missing values and noncompliance. Subjects who had randomization codes generated due to purely technical errors in operating the database will be excluded from any analysis. Subjects who died before receiving either study treatment will also be excluded from any analysis. Subjects randomized and later found not to meet eligibility criteria will be included in the primary analysis to avoid potential bias due to differential assessment of eligibility. Sensitivity analyses excluding these subjects will be conducted. Subjects who were randomized into the wrong stratum will be analyzed as per-randomization strata. All analyses will use 2-sided tests and an overall significance level of 0.05 as the threshold for statistical significance. We will report nominal p-values for all analyses.

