## **V. Primary Outcome Analysis**

The primary endpoint of the study is whether or not the subject is alive and capable of walking 10 feet or across a room without human assistance at 60 days post-randomization. As per the study protocol, the day 60 assessment will be performed within a window of 31-90 days post-randomization, although every effort will be made to make the assessment as close to day 60 as

possible. Results of assessments performed outside the 31-90 day window will be considered as missing data. The treatment effect will be evaluated using the Mantel-Haenszel (MH) test for difference in proportions, stratified by sex, fracture type, and country. The MH relative risk (RR) of spinal anesthesia (SA) vs. general anesthesia (GA) will be reported. *The Breslow-Day test* (Breslow and Day, 1980) will be used to test homogeneity of the RRs across strata. If there is statistically significant heterogeneity, we will report separate RRs within strata.

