#### **V.1. Sensitivity Analysis for Missing Data**

Baseline characteristics of patients with missing primary outcome will be compared with the baseline characteristics of those included in the analysis to assess potential for bias based on these missing values.

The primary analysis will use complete data, excluding individuals without outcome data. To assess the potential for bias incurred by ignoring the missing data, we will conduct a sensitivity analysis under the assumption of missing at random (MAR) using the inverse-probability-weighting (IPW) method (Hogan and Lancaster, 2004). In the calculation of the M-H RR and test statistic, each subject will be weighted by the inverse probability of being a complete case. We will use the non-missing rate of the primary outcome within each treatment and each stratum to estimate this probability.

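### Must site, a randomization factor, be brought into the Mantel-Haenszel analysis because sparse sites do not make that impossible?

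*SAP*

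**What the plan says.** SAP Section IV states that "Sex, fracture type, and site were the original stratification factors for randomization assignment". It gives the number of sites as 46 and concludes that with so many, "some with very few enrolled subjects, it will not be possible to include site in the stratified analysis". Country is added because care and insurance may differ between the U.S. and Canada. The same section fixes this adjustment set for primary, secondary and exploratory analyses alike.

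For site itself, the plan is descriptive: "We will perform descriptive analyses of results by site to see whether there appear to be any major site-specific effects". The modified intention-to-treat analysis comes "with sensitivity analyses performed to assess the potential impact of missing values and noncompliance", and a further sensitivity analysis excludes subjects later found ineligible. No site-adjusted test or estimate is named. On mis-stratification the section says: "Subjects who were randomized into the wrong stratum will be analyzed as per-randomization strata".

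Section V makes the primary analysis an MH test and MH relative risk, "stratified by sex, fracture type, and country".

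**The concern.** Two things look wrong at first. The stated reason does not fit the primary method: sparse strata are a problem for stratum-specific estimates, but MH statistics are built to combine many small tables. And when allocation is blocked within site, an analysis that ignores site reports a standard error that still contains between-site variation which the design has removed. The test is then conservative and some precision goes unused.

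If sites differed a great deal, a real effect could be missed a little more often than necessary. And if the descriptive results by site looked striking, a site-adjusted analysis might be improvised after unblinding.

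**Working it through.** **Inputs from the SAP.** Randomization factors are sex (2), fracture type (2) and site (46), so there are up to 46 × 2 × 2 = 184 randomization strata. Analysis strata are sex × fracture type × country, 2 × 2 × 2 = 8. The test is two-sided at 0.05. The SAP gives no sample size, event rate, block size or between-site spread, so there is no figure of its own to reproduce, and everything numerical below rests on assumptions.

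**Can MH be computed with sparse sites?** In one stratum let n1 and n0 be the arm sizes, n their sum, a and c the events in the two arms, and m = a + c.

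- Test: the numerator is the sum over strata of (a − n1·m/n). Its variance is the sum of n1·n0·m·(n − m)/[n²(n − 1)].
- Relative risk: sum of (a·n0/n) divided by sum of (c·n1/n).

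If a stratum holds only one arm, say n0 = 0, then m = a and n1 = n. The test term is a − a = 0 and both relative-risk terms are 0, so the stratum drops out harmlessly. With one patient per arm and one event, the test term is ±1/2 with variance 1/4, which is McNemar's test. The calculation is therefore possible.

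**Does it behave?** Assumptions: N = 800 or 1600 (on average 800/184 = 4.3 or 1600/184 = 8.7 patients per cell), lognormal site sizes, blocks of 4, control risk about 0.20 or 0.35, between-site SD on the logit scale 0, 0.5 or 1.0, and 2000 replicates. The Monte Carlo error at 5% is √(0.05 × 0.95/2000) = 0.005.

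- 184 strata: null rejection 0.043–0.054; coverage of the 95% interval 0.947–0.958; mean relative risk 1.30 for a true 1.3 and 0.80 for a true 0.8. Cells with both arms held about 98% of patients at N = 1600 and 93–94% at N = 800.
- 8 strata: null rejection 0.047–0.052 at SD 0, 0.043–0.048 at SD 0.5, and 0.032–0.040 at SD 1.0.

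**Where the stated reason does hold.** In those runs about 55 to 95 of the two-arm cells had an arm without events. That defeats several planned steps:

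- the Breslow-Day test of Section V and its follow-up, "If there is statistically significant heterogeneity, we will report separate RRs within strata";
- the weights of Section V.1, "We will use the non-missing rate of the primary outcome within each treatment and each stratum to estimate this probability", which are undefined where an arm within a stratum has no responders;
- the complier risks of Section V.2, estimated by arm in each stratum.

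**What would be gained?** Second set of assumptions: N = 1600, 18% risk, 10% missing, blocks of 4, sites under 20 patients pooled within country, 20,000 replicates, alternative log-OR −0.35.

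| Between-site SD | 0 | 0.3 | 0.5 | 0.8 |
|---|---|---|---|---|
| 95% of sites lie at | one risk | 11–28% | 8–37% | 4–51% |
| Type I error, 8 strata | 5.3% | 5.0% | 4.9% | 4.1% |
| Type I error, pooled sites | 5.2% | 5.0% | 5.1% | 4.8% |
| Power, 8 strata | 66.7% | 67.5% | 67.1% | 65.4% |
| Power, pooled sites | 66.1% | 67.1% | 67.2% | 67.5% |
| Difference (points) | −0.6 | −0.4 | +0.1 | +2.1 |

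At N = 800 (log-OR −0.5) the differences are −1.0, −1.0, −0.2 and +1.0. With sites held fixed and N = 1600, the 8-stratum standard error of the log relative risk is too large by about 0%, 0.2–0.9%, 0.8–1.4% and 2.9–3.9% across the same four SDs.

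**How far would the two answers differ?** At N = 1600 with 10% missing, the two relative risks differ by a median of 1.0–1.3% and a 95th percentile of 2.9–3.7%. The verdict at 0.05 differs in 1.3–1.7% of null trials and 3.6–5.0% of trials under the alternative.

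**The case for a change.** The best case for a change is this. The sentence in Section IV is untrue of the primary method. A randomization factor is left out of every inferential analysis with only a descriptive look, for which no criterion is set. Section III also allows notable baseline imbalances to lead to secondary adjustments. Naming one site-stratified MH analysis now would cost a short paragraph and no data, and would forestall an improvised one.

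The first part stands as a remark on wording: impossibility is too strong for the MH test and relative risk taken alone. The rest does not amount to a defect.

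- The sentence supports one common adjustment set for the whole plan, and for several parts of that plan the reason is right.
- The rule on wrongly stratified subjects creates no tension. It settles how such subjects are classified, and Section VIII classifies sex and fracture type in the same way; it does not promise analysis by site.
- The primary analysis is fixed in advance. A site analysis devised later would be recognizably unplanned and could not displace it.
- An added analysis that does not replace the primary leaves the slightly conservative standard error in place. In the small share of trials where the two verdicts differ, it would also need a rule for reading the disagreement.

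**Conclusion.** No change follows. The reason given for leaving site out is worded too broadly, but using sex, fracture type and country throughout is a fair trade-off. It keeps one set of strata in which every planned step can be carried out, and the primary test holds its level.

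The price is a standard error up to about 1.4% too large at a between-site log-odds SD of 0.5 or less, and 2.9–3.9% too large at SD 0.8. Putting site in, with small sites pooled, would change power by −1.0 to +0.1 points in the first case and by +1.0 to +2.1 in the second. The gain thus appears only if site risks spread as widely as 4–51%.

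These sizes depend on the assumed sample size, event risk, blocks, site sizes, missingness and site spread, none of which the SAP states. The direction does not: in every scenario run the 8-stratum test was valid or conservative, with no inflation beyond simulation error.

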## VI. Secondary Outcome Analyses

VI.1. 60 day mortality. This component of the primary endpoint will be assessed via site reports of deaths and at the day 60 telephone interview, and will be analyzed as a binary outcome using the MH method, stratified by sex, fracture type, and country. Patients who are unable to be assessed directly or by proxy at the 60-day telephone interview but who are known to be alive at later time points will be categorized as alive at day 60. Additional information on deaths prior to day 60 will be obtained via a National Death Index search for patients who were randomized at US sites with sufficient identifying information and for whom no follow-up at or beyond day 60 is available. The Breslow-Day test will be used to assess homogeneity of the RRs across strata.

VI.2. Ability to walk 10 feet without human assistance at 60 days post-randomization. This component of the primary endpoint will be analyzed as a binary outcome, using the MH test stratified by sex, fracture type, and country. Participants who died prior to completing the 60 day interview or had no informative answer to the ambulation assessment will be excluded from the analysis.

VI.3. New-onset delirium. This outcome will be determined by baseline and post-operative 3D CAM tests. Subjects will have a baseline 3D-CAM assessment prior to randomization and assessments on days 1, 2 and 3 post-surgery, with fewer assessments if discharged, withdrawn, or died prior to day 3. Only subjects with a baseline 3D-CAM assessment but no delirium will be included in the analysis. Subjects with a positive response on any post-surgery assessment will be classified as positive for new onset delirium. Subjects who had 1 or more post-surgery assessments with none positive for delirium will be classified as negative for this outcome. Subjects without any post-surgery 3D-CAM response will be excluded from this analysis. This binary outcome will be analyzed using the MH method, stratified by sex, fracture type, and country. The Breslow-Day test will be used to assess homogeneity of the RRs across strata.

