VI.4. Days to hospital discharge. Days from randomization to hospital discharge or death, censored at post-randomization day 30, will be analyzed using a competing risk Cox regression model, adjusted for sex, fracture type, and country (Fine and Grey 1999). The cumulative incidence of hospital discharge will be compared between study arms. The proportional hazards assumption will be assessed using both survival graphs and formal statistical tests of zero slopes in the Schoenfeld residuals and if the proportional hazards assumption is violated, advanced techniques in survival such as incorporating time-dependent covariate effects will be applied (Grambsch and Therneau, 1994; Hess, 1995). Kaplan-Meier curves displaying times to discharge and accounting for competing death risk by study arm will be presented (Pepe and Mori 1993). The interaction between treatment and country will be tested in the Cox model and if the p-value for the interaction test is 0.2 or less, separate analyses by country will be presented.

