## VII. Exploratory Analyses

For all exploratory outcomes, summary statistics (frequencies and percentages for categorical variables, means and standard deviations, or medians and IQRs for continuous variables, frequencies and median time to event for time-to-event variables) will be presented by arm. If there are sufficient events for analysis of binary outcomes, the Mantel-Haenszel relative risk, stratified by sex, fracture type, and country, will be estimated.

**VII.1. Inpatient major morbidity and mortality.** Study site personnel collected data on any of the below events occurring prior to death, discharge, or post-randomization day 30 via medical record review using outcome definitions listed in the REGAIN manual of procedures; additional information on postoperative acute kidney injury was obtained by comparison of site-reported pre-randomization creatinine vs peak post-operative creatinine values where available. Except where specified below, all morbidity and mortality endpoints will be analyzed as binary data.

- a. In-hospital death
- b. Myocardial infarction
- c. Troponin elevation without diagnosed myocardial infarction
  - i. Note: Information on peak postoperative troponin values was collected from REGAIN patients based on laboratory data obtained as a component of routine care. Information on isolated troponin elevation (i.e. without a diagnosis of myocardial infarction) will be reported for individuals not otherwise identified as having experienced a myocardial infarction.
- d. Non-fatal cardiac arrest
- e. Stroke
- f. Pneumonia
- g. Pulmonary embolus
- h. Pulmonary edema
- i. Unplanned postoperative intubation or need for mechanical ventilation
- j. Acute kidney injury
- k. Surgical site infection
- l. Urinary tract infection
- m. Any postoperative transfusion
- n. Any return to OR
- o. Need for critical care admission
- p. Fall within 12 hours of anesthesia

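### The SAP sets an overall 0.05 level for all analyses but reports unadjusted p-values, so the 5% rate holds for the primary test only

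*SAP*

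**What the plan says.** Section IV (General Principles) sets the inference rule in two adjacent sentences: "All analyses will use 2-sided tests and an overall significance level of 0.05 as the threshold for statistical significance", and then "We will report nominal p-values for all analyses". The scope of all analyses is given at the start of the same section: "All analyses (primary, secondary, exploratory) will adjust for the 2 binary stratification factors".

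The comparisons that fall under this rule are set out later:

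- **Primary (section V):** one endpoint and one stratified test. "The treatment effect will be evaluated using the Mantel-Haenszel (MH) test for difference in proportions, stratified by sex, fracture type, and country".
- **Secondary (section VI):** four outcomes, namely 60-day mortality (VI.1), walking at 60 days (VI.2), new-onset delirium (VI.3) and days to hospital discharge (VI.4). Each has a between-arm comparison. For VI.2, for example, "This component of the primary endpoint will be analyzed as a binary outcome, using the MH test stratified by sex, fracture type, and country"; for VI.3, "This binary outcome will be analyzed using the MH method, stratified by sex, fracture type, and country"; for VI.4, "The cumulative incidence of hospital discharge will be compared between study arms".
- **Exploratory (section VII):** 22 listed items. For the binary ones the commitment is to estimation: "If there are sufficient events for analysis of binary outcomes, the Mantel-Haenszel relative risk, stratified by sex, fracture type, and country, will be estimated".

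No section gives a hierarchy, a division of alpha or an adjustment for multiple outcomes.

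**The concern.** A significance level described as overall is commonly read as the error rate across the set of tests it governs. Here that set is every analysis in the plan, yet each p-value is unadjusted and compared with 0.05. Beyond a single test, those two statements do not fit together.

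A milder reading does not remove the problem. If overall means only one common cut-off, section IV still gives a positive rule that a secondary result with p<0.05 is statistically significant, with no caveat.

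What is at stake is how the secondary results are presented. Mortality and delirium will draw attention whatever the primary result shows, and more so if it is null. Under the present wording, one nominal p<0.05 among them could be reported as significant at an overall 5% level.

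**Working it through.** **Inputs.** Per-test level 0.05, two-sided, p-values unadjusted (section IV). Number of tests: 1 primary (section V) and 4 secondary (VI.1 to VI.4), so k = 5. All null hypotheses are taken as true. The SAP gives no correlations between test statistics, so those used below are assumptions.

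**Step 1: the plan's own figure.** For k independent tests at 0.05, the chance of at least one false positive is 1 − 0.95^k. With k = 1 (primary only) this is 1 − 0.95 = 0.050. The stated 5% is reproduced exactly for the primary test.

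**Step 2: the wider set, independent tests.**

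- Four secondary outcomes: 1 − 0.95^4 = 1 − 0.8145 = 0.1855.
- Primary plus four secondary: 1 − 0.95^5 = 1 − 0.7738 = 0.2262.
- Upper bound for the five under any dependence: 5 × 0.05 = 0.25.

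**Step 3: allowing for correlation.** Mortality and walking are components of the primary endpoint, so independence is too pessimistic. Five standard normal statistics with common correlation ρ were simulated (400,000 draws), as √ρ·g + √(1 − ρ)·e with g shared and e separate. The proportion of draws with any |z| > 1.96 was:

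| Assumed ρ | Chance of at least one false positive |
|---|---|
| 0 | 0.226 |
| 0.3 | 0.210 |
| 0.5 | 0.183 |
| 0.8 | 0.128 |

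The ρ = 0 row agrees with the formula in step 2. The rate would fall to 0.05 only if all five statistics were identical (ρ = 1), that is, a single test.

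**Step 4: what a literal overall 5% would need.** For these five tests, a simple Bonferroni split gives 0.05/5 = 0.010 per test. The SAP specifies neither this nor any other procedure.

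**The case against.** The strongest reply is that the SAP never promises family-wise control. It does not use that term. Overall can mean one general threshold, and the very next sentence says openly that p-values are nominal. One primary endpoint, with labelled secondary outcomes reported at nominal p-values, is an accepted design. The word may also refer to interim looks, which a protocol would normally describe. This SAP describes none, so that cannot be settled from it.

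Much of this stands. It shows that the sentence is ambiguous, and that the SAP does not plainly assert control across outcomes. But disclosing that p-values are nominal does not say what may be concluded from them. The preceding sentence does say so, for all analyses.

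Three stronger readings are tempting, and the SAP does not support them:

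- **That the primary result is at risk.** It is one test at 0.05, with exactly that error rate.
- **That 0.05 is applied to every p-value.** The treatment-by-country interaction in VI.4 and the nine subgroup interaction screens in section VIII use 0.20.
- **That the calculation should run over all 27 listed outcomes (1 + 4 + 22).** For binary exploratory outcomes, section VII promises only a relative risk estimate, if events suffice, and names no test. The discharge-location model is also conditional on numbers, and the disability score is marked optional. Several outcomes count overlapping deaths. A figure built on 27 independent tests would describe tests that the plan does not commit to.

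**Conclusion.** The concern holds as a defect in a stated rule, limited to what may be claimed outside the primary test. Section IV attaches an overall 5% level to all analyses, while the plan delivers 5% for the primary test alone. Over the primary and four secondary outcomes the rate is 22.6% under independence, and about 13% to 21% at assumed common correlations of 0.8 to 0.3. These figures assume that all five nulls are true and that one correlation applies to every pair. The second is a simplification, because the two components of the primary endpoint will be more closely tied to it than discharge time is. A reader might infer that the trial's main conclusion is weakened; it is not. The change is worth making before unblinding because it settles which secondary findings may be called significant.

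**What to change.** Replace the two sentences in section IV with wording to this effect: the primary outcome is tested at a two-sided 0.05 level; secondary, exploratory and subgroup results are reported as estimates with 95% confidence intervals and any nominal p-values, are not adjusted for multiplicity, and will not be declared statistically significant.

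Section V makes stratum-specific relative risks depend on a significant Breslow-Day test and takes its cut-off from section IV. The new wording should therefore keep an explicit level for that check.

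If the sponsor wants confirmatory claims on secondary outcomes, a named procedure such as Holm across the four, after a significant primary test, would supply them. That is optional and not needed to correct the defect.

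The cost is SAP wording only, with no change to data, sample size or the primary analysis. The real downside is that a secondary result with nominal p<0.05 cannot be claimed as significant.
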